#### **Inclusion criteria**

Patient's records with the following characteristics:

- Patients over 18 years of age
- Patients of both genders
- Patients diagnosed with COVID-19 infection
- Patients admitted to hospital
- Complete file

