#### **Problem statement**

The first case of COVID-19 in Mexico was reported on February 27, 2020, currently our country has 27.2 cases per 100,000 habitants. According to the Ministry of Health, there are currently 36,327 confirmed cases of COVID-19 in the country with a total of 3,573 deaths. The WHO reports in the month of May, Mexico presented a case fatality rate (CFR) of 12%, being one of the highest reported during the SARS-COV 2 pandemic. COVID-19 has a wide range of clinical manifestations, ranging from asymptomatic to severe ARDS that requires invasive mechanical ventilation. According to Chinese reports, not all severe cases of COVID-19 required admission to the ICU, in Italy 12% of positive patients required admission to the critical care unit. In Mexico it has been observed that 56% of the patients who required intubation for severe management of the disease die, on the other hand, in China, 49% of the patients with a severe picture of COVID-19 died. In a multicenter study during the early outbreak in Wuhan 97% of the patients who required invasive mechanical ventilation died, although mortality could be affected by medical practice in each region. It seems important to highlight that several patients who require intubation are in a high risk of dying. There are some comorbidities related to an increased mortality such as hypertension, diabetes, vascular diseases, COPD and cancer, highly prevalent diseases in the Mexican environment. Mortality in patients with mechanical ventilation is striking, it makes us wonder if the ventilatory management per se generates complications that lead the patient to death, such as Ventilator-Induced Lung Injury (VILI), hemodynamic repercussion due to positive pressure or the fact that intubated patients are simply more critically ill patients. Another current issue that has been observed internationally is the lack of medical equipment due to the high demand for patients. One of the strategies that have been reproduced internationally is the placement of prone patients early in awake patients without mechanical ventilation, with encouraging preliminary results.

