#### Justification

COVID-19 is a pandemic that has significantly challenged health systems worldwide. Due to the large number of infections around the world, the implementation of strategies to reduce the number of intubations and the need for invasive mechanical ventilation becomes important. In addition to the inability of the Mexican health system to respond, patients under invasive ventilation have not had a favorable survival outcome. Up to 97% mortality has been reported in patients requiring intubation. The exact cause of this poor prognosis is not yet known. Early recognition of hypoxemic patients could help with the results. It seems reasonable in these patients to perform procedures to improve the clinical respiratory picture before intubation in less severe cases due to the quoted above. Prone patient placement during invasive mechanical ventilation is a widespread practice in the management of severe ARDS of other etiologies. Currently, few attempts have been made to implement the prone position in patients who spontaneously ventilate with supplemental oxygen, high-flow nasal cannulas, or noninvasive mechanical ventilation. Taking into account that it is a procedure that does not require additional infrastructure within the services and does not represent an additional cost for its implementation, it becomes a valuable tool in the context of COVID-19 where intubation is associated with high mortality, additionally there are mechanical ventilator deficits in most hospitals. This work has feasibility to be carried out because it will be carried out in critical areas that have equipment and trained personnel for it in the different shifts, in addition to having patients diagnosed with COVID-19.

**Null hypothesis (H0):** In patients diagnosed with COVID-19 infection, there is no relationship between the awaken prone positioning and orotracheal intubation.

Alternate hypothesis (H1): In patients diagnosed with COVID-19 infection, there is a relationship between the awaken prone positioning and the need for orotracheal intubation.

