### **Exclution criteria**

- Files not found.
- Patients who do not decide to participate in the study.

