#### **Elimination criteria**

- Files with incomplete data
- File with a voluntary discharge form or transfer note.

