# Independent variable

Variable	Conceptual definition	Operational definition	Туре	Measurement scale (years)	
Age	Time elapsed from the birth of a person to a certain moment.	The age recorded in the clinical record at the patient's admission to the hospital will be considered.	Discrete quantitative	
 
18 a 27
 
28 a 37
 
38 a 47
 
48 a 57
 
58 a 67
 
68 a 77
 
78 a 87
 
88 a 97
 
997
 
	
Gender	Social concepts of functions, behaviors, activities and attributes for men and women.	Gender that is registered in the clinical record	Qualitative nominal	Male Female	
Prone position	What is called the prone position	Record in the record of the placement of the patient in the prone position for a minimum of 2 hours.	Qualitative	Nominal (dichotomous): Yes No	
Type of oxygen support supplied	Device used for supplemental oxygen administration.	Record in the clinical record of the type of oxygen supplied.	Qualitative nominal	
 
Nasal cannulas
 
High flow nasal cannulas
 
Face mask
 
Other
 
	
Partial oxygen saturation index (SpO2) / inspired oxygen fraction (FiO2)	Resulting index for SpO2 / FiO2 ratio	2 index records will be taken at admission and the second after the patient's prone position, recorded in the clinical record.	Discrete quantitative	1. 100 a 150 2. 151 a 200 3. 201 a 250 4. 251 a 300 5. 301 a 350	

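### Eligibility requires neither hypoxaemia nor supplemental oxygen, although the rationale and data scales presume it; room-air patients in the non-prone group could mask or reverse a prone effect in the unadjusted relative risk

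*Protocol*

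**What the plan says.** **Who enters.** Inclusion criteria (Protocol) lists adult age, either gender, "Patients diagnosed with COVID-19 infection", "Patients admitted to hospital" and "Complete file". The exclusions are missing files and "Patients who do not decide to participate in the study". Elimination criteria removes incomplete data and "File with a voluntary discharge form or transfer note". Study population repeats the diagnosis alone. None of these sections mentions oxygenation or oxygen support.

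**Whom the rest of the protocol has in mind.** The title refers to oxygen therapy. The studies in Theoretical framework concern hypoxaemia, respiratory failure or ARDS. Justification argues that "few attempts have been made to implement the prone position in patients who spontaneously ventilate with supplemental oxygen, high-flow nasal cannulas, or noninvasive mechanical ventilation". In the Independent variable table, oxygen support is defined as "Device used for supplemental oxygen administration", with levels for nasal cannulas, high-flow cannulas, face mask and other. The highest SpO2/FiO2 band is 301 to 350. Problem statement describes the disease as "ranging from asymptomatic to severe ARDS that requires invasive mechanical ventilation".

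**What is compared.** Exposure is recorded proning for at least 2 hours, yes or no. The outcome is intubation for any cause during the stay. Statistical analysis sets one against the other by contingency table, relative risk with 95% CI, and a chi-square or Fisher test. It states no stratification or adjustment of that relative risk. A separate linear regression lists the SpO2/FiO2 index among its variables but not the oxygen device.

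**The concern.** An adult admitted with mild disease and breathing room air meets the listed clinical criteria. Such a patient has little reason to be proned and a low risk of intubation. Anyone without 2 recorded hours of proning counts as not prone, so this patient would usually land in the cell for neither proned nor intubated.

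That lowers the comparator's intubation risk for reasons unrelated to proning. Proned patients are likely to be more hypoxaemic than unproned ones under any entry rule in an observational cohort, and an entry rule with no oxygenation floor widens the gap. Since the relative risk is the only effect measure named for the main objective, a real benefit could be reported as no association, or an absent effect as harm.

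**Working it through.** **1. The plan's own figure.** Sample size calculation uses N = 8463, Z = 1.96, p = q = 0.5 and E = 0.05:

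n = 8463 × 3.8416 × 0.25 / (8462 × 0.0025 + 3.8416 × 0.25) = 8127.87 / 22.115 = 367.5, rounded up to 368.

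The stated 368 is reproduced and is not in dispute. It is a precision calculation for one proportion and carries no assumption about intubation risk by group, so it cannot supply inputs for the check below.

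**2. Do the coding scales fit the entry rule?** With FiO2 0.21 on room air:

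- Top of the highest band: 350 × 0.21 = 73.5, so any room-air SpO2 above 73.5% is off the scale.
- Example: SpO2 95% gives 95 / 0.21 ≈ 452.

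The inclusion criteria therefore admit patients whom the SpO2/FiO2 scale cannot code.

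**3. Effect on the relative risk.** All inputs here are assumptions:

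- Intubation risk in non-proned patients on oxygen: 0.35. The nearest figure in the protocol is the 50-patient emergency-department series in Theoretical framework (saturation below 90% on admission, early proning), where 64% avoided intubation, so 36% did not.
- Risk on room air: 0.02.
- Room-air patients are never proned and form a share f of the non-prone group.
- Patients on oxygen have the same underlying risk in both groups.

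Non-prone risk = (1 − f) × 0.35 + f × 0.02. Crude RR = 0.35 × true RR / non-prone risk, so the numerator is 0.245 when the true RR is 0.70.

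| f | Non-prone risk | Crude RR, true RR 0.70 | Crude RR, true RR 1.00 |
|---|---|---|---|
| 0 | 0.350 | 0.70 | 1.00 |
| 10% | 0.317 | 0.77 | 1.10 |
| 30% | 0.251 | 0.98 | 1.39 |
| 50% | 0.185 | 1.32 | 1.89 |

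A true RR of 0.70 is fully masked (crude RR = 1) at f = 0.30 × 0.35 / (0.35 − 0.02) = 0.105 / 0.33 ≈ 32%.

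**4. Sensitivity.** With risks of 0.36 to 0.50 on oxygen and 0 to 0.05 on room air, the masking share is 30% to 35% for a true RR of 0.70 and 20% to 23% for a true RR of 0.80. The result depends mainly on f and little on the assumed risks.

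**5. What drives it.** The distortion comes from imbalance between the groups. If room-air patients were 30% of both groups, with the same RR of 0.70 on room air, the crude RR would be (0.7 × 0.245 + 0.3 × 0.014) / 0.251 = 0.1757 / 0.251 = 0.70. Assuming that none are proned is thus the extreme case in this respect.

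**The case against.** Several points on the other side stand.

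- **The stated question is broad.** Research question, both hypotheses and Study population all speak of patients diagnosed with COVID-19. A reader might infer that room-air patients lie outside the study question, but the documents do not support that. The conflict is with the rationale and the scales.
- **Handling of room-air files is ambiguous.** A reader might infer that every hospitalised adult with COVID-19 enters. A complete file is required, and files with incomplete data, transfers and voluntary discharges are removed. A room-air file with no codable oxygen device or index might be dropped as incomplete, or coded as other. Justification also places the work in critical areas, though as a feasibility remark. The protocol settles none of this, so sites could differ.
- **The entry rule does not create confounding by indication.** That arises because proning was not randomised. The entry rule makes it worse. Nor does the protocol state why patients were proned.
- **Adjustment may help.** SpO2/FiO2 is recorded at admission and listed in the regression, so it cannot be said that analysis could not repair the problem. But that model is separate from the relative risk, is specified as linear and omits the oxygen device.
- **The illustration models one bias.** Theoretical framework says awake proning is possible on room air, so some such patients may be proned. A patient intubated before completing 2 hours prone counts as not prone and intubated, which pushes the RR the other way.

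A statistical analysis plan, not shown, might define an analysis population. Eligibility and the coding scales are fixed in the protocol, however, and there they disagree.

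**Conclusion.** The point holds as a should-fix. The inclusion criteria set no oxygenation or oxygen-support condition, the scales presume one, and the relative risk is stated without adjustment. Followed as written, the plan can produce a misleading main result. Under the assumed 35% and 2% risks, about one third of room-air patients in the non-prone group is enough to hide a true RR of 0.70, and half is enough to reverse it.

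The size rests wholly on assumptions, because the documents give neither the share of room-air patients nor the intubation risk by group. A reader might infer that the reported relative risk will be biased upwards. The calculation shows only that it can be. The net direction across all selection effects is undetermined.

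**What to change.** 1. **Restrict.** Limit eligibility, or the primary analysis population, to patients receiving supplemental oxygen and not intubated at a defined baseline such as admission. Apply the same rule at the same time point to proned and non-proned patients. Any hypoxaemia threshold is for the investigators to set.
2. **Make the other patients codable.** Add a none/room-air level to oxygen support and an SpO2/FiO2 class above 350, state that such files are not incomplete on that account, and describe these patients separately.
3. **Adjust.** Stratify or adjust the primary relative risk by baseline SpO2/FiO2 and oxygen device. Restriction alone would still compare patients on low-flow cannulas with patients on high-flow support.

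**Cost.** One eligibility line or population definition, two added category levels and one analysis statement. Oxygen support and initial SaO2/FiO2 are already on the Information gathering instrument, and this is a record review. The price is that results apply only to patients on oxygen, and room-air files, including any patients proned on room air, leave the primary comparison and may need replacing to reach 368. Confounding by indication is reduced but not removed.

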### **Exclution criteria**

- Files not found.
- Patients who do not decide to participate in the study.

#### **Elimination criteria**

- Files with incomplete data
- File with a voluntary discharge form or transfer note.

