#### Variables categorization

The source of collection of the variables will be the clinical file.

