#### Information gathering instrument

Case	Gender	Age	Comorbidities	Type of oxygen support supplied	Pharmacotherapy	Awake prone position (Yes/no)	Time of Awake prone position (hours)	Initial SaO2/FiO2	SaO2/FiO2 before to the prone position	Prone position (hours)	Intubation Yes/No

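### An undefined completeness rule discards files whose prone and intubation status are both known, and can bias the relative risk

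*Protocol*

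**What the plan says.** Completeness is required twice. The protocol's Inclusion criteria list "Complete file", and its Elimination criteria list "Files with incomplete data". Neither section says which items make a file complete. Under Variables categorization, "The source of collection of the variables will be the clinical file", so an incomplete file most naturally means one lacking a study variable.

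Some of those variables depend on exposure:

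- The Independent variable table defines exposure as "placement of the patient in the prone position for a minimum of 2 hours".
- For the SpO2/FiO2 index, the same table says "2 index records will be taken at admission and the second after" proning.
- The Information gathering instrument has two columns for hours in prone and a column headed "SaO2/FiO2 before to the prone position". It has no column for an index after proning.

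The Statistical analysis section bases the main comparison on a relative risk with a 95% confidence interval and a chi-square or Fisher test of intubation against prone position.

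**The concern.** A main analysis that uses two binary items does not need a full record. If a file without, say, a comorbidity entry or a second index reading leaves the whole study, a known exposure and a known outcome are thrown away.

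The loss need not be neutral. An index after proning can exist only if the patient was proned, and it may not be obtained if intubation comes first. A patient who was prone for at least 2 hours and was then intubated before that reading would have an incomplete file because of both exposure and outcome. Removing such files takes events out of the prone group only.

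Because this is a stated eligibility rule, a later analysis plan cannot recover files that never entered the dataset.

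**Working it through.** **The plan's own figure.** Under Sample size calculation, N = 8463, Z = 1.96, p = q = 0.5 and E = 0.05.

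n = N·Z²·p·q / [(N−1)·E² + Z²·p·q] = (8463 × 0.9604) / (8462 × 0.0025 + 0.9604) = 367.52, rounded up to 368. The figure reproduces. The protocol does not say whether 368 counts files before or after elimination.

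**Effect of selection on the relative risk.** Let p1 and p0 be the true intubation risks in proned and unproned patients. Let k1i and k1n be the fractions of proned files kept among intubated and non-intubated patients, and k0i and k0n the same for unproned files. The observed risks are

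p1′ = p1·k1i / [p1·k1i + (1−p1)·k1n], and likewise p0′; observed RR = p1′/p0′.

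The protocol gives no retention rates, so every k below is an assumption, as is p1 = p0 = 0.40 (no true effect).

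| Files kept (all other cells 100% unless stated) | p1′ | p0′ | RR |
|---|---|---|---|
| 80% of proned, intubated | 0.32/0.92 = 0.348 | 0.400 | 0.87 |
| 70% of proned, intubated | 0.28/0.88 = 0.318 | 0.400 | 0.80 |
| 50% of proned, intubated | 0.20/0.80 = 0.250 | 0.400 | 0.63 |
| 70% of unproned, intubated; 90% in the other three cells | 0.36/0.90 = 0.400 | 0.28/0.82 = 0.341 | 1.17 |

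**When there is no bias.** Under no effect the RR stays at 1.00 whenever k1i/k1n = k0i/k0n.

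- Loss that depends on prone status alone (40% of unproned files lost) leaves RR at 1.00.
- Loss that depends on intubation alone (30% of intubated files lost) also leaves RR at 1.00 under no effect. It moves a true RR of 0.80 (40% against 50%) to (0.28/0.88)/(0.35/0.85) = 0.77.

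**Sensitivity to the assumed risk.** At 36% intubation, implied by the series in the Theoretical framework in which 64% avoided it, losing 20% of proned, intubated files gives RR 0.86. With 184 files per group (assumed), the chance of a false finding in favour of prone rises from 2.5% to about 17%. At 50% intubation the figures are RR 0.89 and 18%.

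**Loss of files without bias.** The form has 11 data columns besides the case number. If each is missing independently with probability m, the share of files lost is 1 − (1−m)^11: 20%, 28% and 43% for m = 2%, 3% and 5%. Two of the 11 are prone and intubation status, without which a file is unusable under any rule. Among files where both are readable, the loss is 1 − (1−m)^9: 17%, 24% and 37%. Three of the remaining nine columns apply only to proned patients, so the loss is smaller for unproned patients if those columns count as not applicable.

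**The case against.** The strongest reply is that nothing says one missing item removes a file. An abstractor would ordinarily treat a field that does not apply as not missing. A reader might infer that the rule removes every unproned patient, since none can have a prone-related index. The documents do not support that: the Main objective, the Specific objectives (which describe proned and unproned patients) and the Statistical analysis section all need an unproned group. This part of the objection stands.

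The early-intubation route is also narrower than it first appears. Exposure requires at least 2 hours prone, so a patient intubated sooner is not in the prone group. The form asks for an index before proning and not after it, contrary to the Independent variable table. If completeness is judged on the form alone, an intubation after proning does not make that index missing, and the route largely disappears. No passage shows how often the later reading is absent.

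The first three rows of the table also put all the loss in one cell, which is an unfavourable arrangement, and the independent-missingness figures describe lost precision, not bias. Even that loss matters only if eliminated files are not replaced. Multiple imputation is a choice that an analysis plan may properly make.

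None of this defines completeness or explains why a two-variable comparison needs it. Under the present text each abstractor must decide which files to drop, with intubation status recorded on the same form.

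**Conclusion.** The point holds as a defect in a stated rule. Completeness is an eligibility and elimination criterion, it is undefined, and on its natural reading it discards files in which prone and intubation status are both known. The rule can bias the relative risk, and under no true effect it does so only if completeness depends on prone status and intubation jointly.

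A reader might infer that the rule will make awake prone look protective. The documents do not support that. They give no rate of incomplete files by group, and plausible patterns run either way: 0.87 with 20% of proned, intubated files lost, and 1.17 under the opposite pattern. These figures rest on an assumed 40% risk and assumed retention rates, and they show what could happen, not what will. The Independent variable table and the form also disagree on whether the second index comes before or after proning, and this affects which files count as incomplete.

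**What to change.** - Replace "Complete file" and "Files with incomplete data" with a requirement that prone status and intubation status can be read from the file. Run the main relative risk on every otherwise eligible file that meets it.
- Mark prone hours and prone-related index values as not applicable for unproned patients, so that their absence is not counted as missing.
- Reconcile the Independent variable table with the Information gathering instrument on whether the second index is recorded before or after proning.
- Handle missing covariates only within the adjusted and secondary analyses, for example by multiple imputation with the complete-file analysis as a sensitivity check.
- Report the number of incomplete files by prone and intubation status, so that readers can judge whether selection was differential.

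The cost is a change of protocol wording and a little more analysis work. If imputation is used, it adds a missing-at-random assumption for covariates only; the main comparison does not rely on it.

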#### **Study population**

Patients diagnosed with COVID-19

#### Variables categorization

The source of collection of the variables will be the clinical file.

#### Dependent

Variable	Conceptual definition	Operational definition	Туре	Measurement scale
Orotracheal intubation	Placing a probe into the trachea through the mouth or nose to connect to a mechanical ventilator.	Performing intubation for any cause or non- intubation during your hospitalization.	Qualitative	Nominal (dichotomous): Yes No

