#### Statistical analysis

Descriptive statistics, measures of central tendency, measures of dispersion and standard deviation will be used.

While for the qualitative variable's frequency measures (relative, absolute and percentage) were used. Relative risk will be performed with a 95% confidence interval of significance (95% CI) and contingency tables.

For inferential statistics, the difference in proportions between the dependent (orotracheal intubation) and independent (prone position) variables will first be verified based on the number of expected observations (<5) Fisher's exact test or (> 5) Chi square test, contrasting H0:  $\phi = 1$ , taking p <0.05 as a statistically significant value.

A multivariate analysis will be used to generate linear regression models with the different variables: prone time, age, gender and orotracheal intubation, SpO2 / FiO2 index in order to explain their interactions (if the time in prone, age or gender affects the main objective) as well as adopting the best model that matches the observations (best R2, AIC) as a predictive model.

The results will be presented in graphs and / or tables as appropriate.

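### A death without intubation is counted as no intubation and vital status is not collected, so the main comparison cannot separate averted intubation from death before intubation

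*Protocol*

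**What the plan says.** The protocol's Main objective is to relate awake proning to the need for intubation. The Dependent variable table defines the outcome operationally as "Performing intubation for any cause or non- intubation during your hospitalization", on the scale "Nominal (dichotomous): Yes No". There is no third level and no rule for a patient who dies first.

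The Elimination criteria remove incomplete files and any "File with a voluntary discharge form or transfer note". They do not remove deaths. The independent and confounding variable tables do not list death or discharge status. On the form under Information gathering instrument, the outcome column is "Intubation Yes/No", and no column holds vital status.

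Under Statistical analysis, "the difference in proportions between the dependent (orotracheal intubation) and independent (prone position) variables will first be verified" by Fisher's exact or chi-square test, "taking p <0.05 as a statistically significant value". A relative risk with 95% confidence interval accompanies the test.

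On context, the Justification says "additionally there are mechanical ventilator deficits in most hospitals", and the Problem statement says "Another current issue that has been observed internationally is the lack of medical equipment due to the high demand for patients".

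**The concern.** Death before intubation is a competing event: once it happens, intubation can no longer be observed. With a two-level outcome over the whole stay, that patient can only be a No. A No therefore mixes two very different courses, recovery without a tube and death without one.

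The objective asks about need. Where ventilators are short, a patient may need intubation and not receive it, so intubation carried out is an imperfect stand-in for need. Proning is not assigned in this study, so nothing makes un-intubated deaths equally common in the two groups. If they are not, the relative risk can move away from 1 with no effect of proning on deterioration, or stay at 1 when there is an effect. The data set as specified could not show which had happened. The Ethical considerations say that the work is meant to favour use of awake proning, so a difference of this kind would matter to readers.

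**Working it through.** **1. The plan's own figure.** Under Sample size calculation, n = N z² p q / [(N − 1) E² + z² p q], with N = 8463, z = 1.96, p = q = 0.5 and E = 0.05. The numerator is 8463 × 3.8416 × 0.25 = 8127.87. The denominator is 8462 × 0.0025 + 0.9604 = 22.1154. The ratio is 367.5, rounded up to 368. The stated 368 is reproduced and is not in dispute; it serves below only as the study size.

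**2. How an un-intubated death is coded.**
- The outcome has two levels, covering the hospital stay (Dependent table).
- Deaths stay in the analysis (Elimination criteria).
- No other variable or column identifies them (variable tables and form).

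The protocol does not say in words that such a death is a No, but its definition leaves no other code.

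**3. Effect on the relative risk.** The documents give no rate of un-intubated death and no group sizes, so all rates here are assumptions. Let c be the risk of being intubated or dying un-intubated, and d the risk of dying un-intubated. Recorded intubation is then c − d. Set c = 40% in both groups, so that there is no true difference.

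| d, prone | d, non-prone | Intubated, prone | Intubated, non-prone | Intubation RR | Composite RR |
|---|---|---|---|---|---|
| 12% | 5% | 28% | 35% | 0.28/0.35 = 0.80 | 0.40/0.40 = 1.00 |
| 5% | 12% | 35% | 28% | 0.35/0.28 = 1.25 | 1.00 |
| 10% | 5% | 30% | 35% | 0.30/0.35 = 0.86 | 1.00 |
| 15% | 5% | 25% | 35% | 0.25/0.35 = 0.71 | 1.00 |
| 5% | 5% | 35% | 35% | 1.00 | 1.00 |

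The last row is the case in which no false difference arises.

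**4. How often the planned test would reject.** Assume an even split of the 368 patients (184 per group) and two-sided α = 0.05. The normal approximation to the power is Φ{[|p₀ − p₁| − 1.96 √(2 p̄(1 − p̄)/184)] / √([p₀(1 − p₀) + p₁(1 − p₁)]/184)}, where p̄ is the mean of p₀ and p₁.
- 35% v 28%: (0.07 − 1.96 × 0.04843)/0.04829 = −0.516, probability 0.30.
- 35% v 30%: (0.05 − 1.96 × 0.04883)/0.04876 = −0.937, probability 0.17.
- 35% v 25%: (0.10 − 1.96 × 0.04778)/0.04749 = 0.134, probability 0.55.

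With the composite as outcome, the probability is the nominal 0.05 in each case. For un-intubated deaths of 15% (prone) v 5%, changing c from 30% to 50% moves the RR from 0.60 to 0.78 and the rejection probability from 0.67 to 0.50. An uneven split of 276 non-prone to 92 prone lowers the 0.55 to 0.42.

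**5. The opposite error.** Suppose the composite is 40% non-prone and 30% prone (RR 0.30/0.40 = 0.75), with un-intubated deaths of 10% and 0%. Recorded intubation is 30% in both groups and its RR is 1.00, so a real difference is hidden.

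**The case against.** The strongest reply is that this is an omission from the form and nothing worse. The study is retrospective, the variables come from the clinical file, and a complete file is required for inclusion. An in-hospital death should normally be found there. This stands: a reader might infer that these deaths are lost for good, and the documents do not support that. Only the data set as now specified lacks them.

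A second reply is that the protocol does not show such deaths to be common at its sites. This also stands. The 12% case fatality rate in the Problem statement is national and covers deaths with and without intubation; the counts there give 3,573/36,327 = 9.8%. It is no source for the 12% used in the illustration. The equipment shortage in that section is described as international. The ventilator deficits in the Justification are general, and the same section says that the work will take place in critical areas with equipment and trained staff. That does not establish that ventilators sufficed, but it leaves un-intubated deaths plausible rather than expected.

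Third, it is tempting to infer that the bias flatters proning. The documents do not support a direction. Proning might be used where intubation is unavailable, which would place un-intubated deaths in the prone group. But the Justification also speaks of acting before intubation in less severe cases, and prone status requires at least 2 recorded hours, so very early deaths would tend to fall in the non-prone group.

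Finally, the hypotheses are non-directional and the table does not call No a favourable result. That is so, but the mixing of two outcomes in one cell does not depend on the label.

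A separate analysis plan could choose a composite or a competing-risk method. It could not apply either to a data set that holds no vital status.

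**Conclusion.** The point holds in limited form. The outcome as defined counts an un-intubated death together with a recovery, and the specified data cannot separate them, although the objective concerns the need for intubation. The main relative risk is biased by this if un-intubated deaths differ by prone status. In the assumed scenarios with c = 40%, it runs from 0.71 to 1.25 where the composite is 1.00. These figures show what can happen; they do not estimate what did. Equal un-intubated death rates with no prone effect give no false difference, but without vital status nobody could show that this condition was met.

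A reader might go further and hold that benefit may be concluded only if the composite agrees. The documents do not call for such a rule in an observational study of association; the two results should be read together.

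**What to change.** Add one item, vital status at end of stay (discharged alive or died), to the variable list and to the form, taken from the clinical file that is already being read. State in the Dependent variable table how death without intubation is handled. Then:
- report un-intubated deaths by prone status;
- report intubation or in-hospital death, with the same relative risk, 95% confidence interval and test, beside the planned intubation analysis;
- interpret the intubation result in the light of both.

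The cost is one more data item per file and one more 2×2 table, and the planned analysis stays as it is. The downside is small: the composite will include some deaths unrelated to respiratory failure. The change does not address confounding between proned and non-proned patients.
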